## Matching:

Logistic regression will be used to estimate propensity scores (PS). The logit function may include, among others, age, sex, index date (prescription date of conventional systemic therapy), and the presence of at least one cardiovascular risk factor. However, we intend to use clinical judgment to determine which variables will be added based on standardized differences. For matching, we are considering nearest-neighbor (greedy) matching with a 1:1 to 1:4 ratio—likely with replacement. We intend to use a caliper of  $\pm 0.01$  but have also considered  $0.2 \times \text{SD of logit(PS)}$ . Depending on performance, “optimal” matching could also be considered instead. The model with the best properties will be applied. Alternative

approaches for handling matching and assessing model performance are discussed (among others) here.

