## 8. RESEARCH METHODS

### 8.1. Study Design

This is a retrospective register study employing a matched cohort design. This study design was selected to reflect real world usage by utilizing the high-quality registries in Denmark with detailed information on patients with AD. This allows for retrospective analysis of a large number of patients and gives the possibility for comparing with cohort matched control groups (see details below and in section 9.2): the database includes information about close to 13.000 adult patients with a hospital diagnosis of AD. In addition, the database contains information about the general adult population estimated to 4.2 million in 2019. Hence a retrospective study design is more feasible than a prospective design. By matching adult AD patients on conventional systemic therapy with two comparator cohorts – the general Danish population and dermatologist-verified AD patients not receiving systemic treatment – the study contextualizes adverse event rates and isolates the treatment's effect. The general population cohort provides background incidence rates, and the untreated AD cohort helps distinguish the baseline risk from AD itself versus any additional risk due to systemic therapy. Matching on key factors (e.g., age, sex, and cardiovascular risk factors) further enhances methodological rigor by reducing confounding, making the safety outcome comparisons more reliable and clinically meaningful.

Patients with a diagnosis of AD (Table I) are included using the inclusion and exclusion criteria specified in 9.2. AD patients will be matched with individuals from the general population and patients with AD not treated with a systemic to enable relevant comparisons to further investigate safety data in the AD population.

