**Exclusion criteria rationale:**

The aim is to ensure that the adverse events registered cannot be attributed to any current or previous cases of cancer (criteria 1), other treatments (criteria 2 and 3), or other inflammatory diseases and their treatments (criteria 4). Additionally, it ensures that systemic treatments are administered specifically for AD and not for any other condition (criteria 4).

Given the high number of AD patients in the registry combined with previous experience each treatment group it is expected to comprise around 1000 patients for the majority of treatments.

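### For the general-population cohort, the planned propensity-score match has an inert caliper and does not secure age comparability; exact matching would, at almost no cost

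*Protocol*

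**What the plan says.** Protocol section 8.7 (Matching) describes one logistic propensity score and does not distinguish between the two comparator cohorts. The covariates are candidates: "The logit function may include, among others, age, sex, index date (prescription date of conventional systemic therapy"), plus a flag for at least one cardiovascular risk factor. Selection among them is left open: "However, we intend to use clinical judgment to determine which variables will be added based on standardized differences". Greedy nearest-neighbour matching at 1:1 to 1:4, probably with replacement, is under consideration. On the caliper the text reads "We intend to use a caliper of" ±0.01, with 0.2 x SD of logit(PS) as an alternative. The scale of the ±0.01 is not given. The best-performing model is to be used, but the text does not define best.

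The relevant sizes are in section 8.1, where "the database contains information about the general adult population estimated to 4.2 million in 2019", and in section 8.2 (Exclusion criteria rationale), where each treatment group is "expected to comprise around 1000 patients for the majority of treatments". Section 8.1 justifies the design by saying that matching on factors such as age, sex and cardiovascular risk reduces confounding. Section 8.7 then reports incidence rates in the matched background cohort as results and uses that cohort as a Cox comparator. Section 8.2 defines cohort entry for exposed patients only.

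**The concern.** A propensity score suits a comparator of limited size with many confounders. The background cohort is the opposite case. The pool is several hundred times larger than the treated group, and birth year, sex and calendar year are known for everyone.

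Two people with the same score need not have the same age, because age is one term among several in the logit. MACE, malignancy and death rise steeply with age. A control group with the right mean age but a wider spread therefore has a higher expected event rate, because the older tail adds more events than the younger tail removes. Standardized differences in means, the t-test and the Mann-Whitney test are not aimed at spread.

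At stake are the background rates reported beside the drug-specific rates and the tertiary drug-versus-background hazard ratios. The drug-specific rates themselves, which answer the primary and secondary objectives, do not depend on the match.

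There is also a definitional gap. The score uses an index date defined by a prescription that background controls never had.

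**Working it through.** The protocol states no figure for matching quality, so there is none to reproduce.

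**1. Caliper.** Inputs: 4.2 million adults (section 8.1); about 1,000 treated for most drugs (section 8.2). A total of 5,000 assumes five drugs at 1,000 each.

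Mean PS = n / (n + 4,200,000):
- n = 1,000: 0.00024, and 0.01 / 0.00024 is about 42.
- n = 5,000: 0.0012, and 0.01 / 0.0012 is about 8.

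In simulations with 5,000 treated, the largest score ran from about 0.002 to 0.010, so on the probability scale ±0.01 admitted every adult. Where it was checked with 4.2 million controls, nearest neighbours differed by at most about 0.000002 in score, and the 0.2 x SD logit caliper also excluded nobody. The caliper therefore neither protects nor harms.

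**2. Mechanism.** Take equal mean ages, normal ages and an event rate proportional to exp(b x age). The background/treated rate ratio with no drug effect is then exp[b² (SD_pop² − SD_trt²) / 2]. All values here are assumed:
- SD 18 against 15, b = 0.06: exp(0.0036 x 99 / 2) = 1.20.
- The same SDs, b = 0.08: exp(0.0064 x 99 / 2) = 1.37.
- The same SDs, b = 0.10: exp(0.0100 x 99 / 2) = 1.64.
- Treated wider (population 18, treated 20), b = 0.08: exp(0.0064 x (−76) / 2) = 0.78.

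This shows direction only. Real matching also changes the control spread.

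**3. Simulated matching.** Assumptions: 5,000 treated and 4.2 million controls; logistic score on linear age, sex, cardiovascular flag and calendar time of index; 1:1 nearest neighbour with replacement; b = 0.08.

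| Treated age mean/SD | Matched control mean/SD | Standardized difference | Variance ratio | Background/treated rate |
|---|---|---|---|---|
| 49.8 / 14.2 | 49.5 / 16.0 | 0.021 | 0.80 | 1.13 |
| 45.9 / 13.6 | 45.8 / 14.9 | 0.005 | 0.83 | 1.14 |
| 45.6 / 12.3 | 45.7 / 14.9 | −0.002 | 0.68 | 1.31 |
| 41.6 / 12.4 | 41.5 / 13.4 | 0.010 | 0.86 | 1.12 |
| 51.0 / 14.9 | 50.8 / 16.5 | 0.009 | 0.82 | 1.16 |
| 50.5 / 16.1 (equal spread) | 50.2 / 16.3 | 0.019 | 0.97 | 1.01 |

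Over b = 0.06 to 0.10 the ratio in the narrower-spread settings was 1.09-1.39. With a population flat to age 75 and then declining, b = 0.06-0.08 and treated SD about 11.5-15.6, it was 1.25-1.84, with age standardized differences of at most 0.06. At treated SD 17.5 it was 1.13-1.17. The overall range for narrower treated ages is 1.09-1.84. A true hazard ratio of 1 would then read about 1/1.84 = 0.54 to 1/1.09 = 0.92.

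**4. What removes it.** A quadratic age term with an age-by-flag interaction, or a cubic age term, gave 0.94-1.03. Entering age and calendar time in whole years also removed the bias, since the nearest score then usually belongs to the same covariate cell. Exact matching on age, sex, calendar year and flag gave 1.00, matched every simulated treated patient and left at least four controls for 99.9%.

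**The case against.** The strongest reply is that the bias depends on a specification the protocol does not adopt. Section 8.7 never says that age is linear. It leaves the algorithm open and cites references on balance, and functional form and diagnostics are commonly settled in an analysis plan that is not shown here. This stands in part: linear age is an assumption, and its consequences are not a property of the plan. What remains is that the protocol commits the background cohort to a PS match whose intended caliper cannot bind, when a simpler method secures what section 8.1 claims.

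Several stronger readings are tempting and are not supported:
- A reader might infer that the loose caliper causes the age imbalance. It does not. Matched scores were nearly identical, and changing the caliper changed nothing.
- A reader might infer that the drugs will look safer. That requires treated ages to be narrower than the population's. The protocol gives no ages, and section 8.9 allows that prednisolone may have been prescribed for other conditions, so the age spread of its users cannot be presumed.
- A reader might infer that all checks would pass. Section 8.7 (Patient characteristics) reports SD or IQR for all three groups, so a difference in spread would be visible. There is only no stated rule that acts on it.
- The sentence on standardized differences might be read as a balance criterion. It concerns the choice of variables, and no balance threshold is stated.

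A large age gap within pairs is also not bias in itself. With a cubic age term about half of pairs (46-62% in one set of runs) still differed by more than ten years, yet the rate ratio was close to 1.

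**Conclusion.** The point holds in limited form. On the protocol's own sizes, a ±0.01 caliper on the probability scale is inert for the background cohort. Separately, a PS match does not guarantee comparable ages. With linear age and a continuous index date, mean age can balance while spread does not.

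If treated ages are narrower than the population's and event rates rise 6-10% per year of age, the background rate could be about 9-84% too high. The bias is near zero with equal spread or a flexible age term, and reversed if treated ages are wider. Both size and direction rest on assumed age distributions.

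The effect is confined to the background rates and the tertiary background comparison, where p-values are descriptive. The change is worth making because it is cheap and also gives controls a defined index date. It is not a reason to doubt the drug-specific rates.

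**What to change.** In section 8.7 (Matching), for the general-population cohort only, replace the PS match by exact matching, for example 1:4, on birth year, sex, calendar year of index and the cardiovascular risk-factor flag. Draw controls from adults who are alive, resident and eligible on the treated patient's index date, and assign them that date.

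Keep the PS for the untreated-AD cohort, with a flexible age term (such as a spline), the 0.2 x SD logit caliper already mentioned, and variance ratios or age-band distributions checked alongside standardized differences.

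The cost is protocol wording and a simple matching program. No further data are needed, and a few treated patients may have fewer than four controls.

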**Patient characteristics:**

Descriptive statistics will be presented to describe patient characteristics performed for all groups:

- a) dermatologist-verified adult patient population with atopic dermatitis (AD) receiving conventional systemic treatments as per inclusion/exclusion criteria,
- b) cohort-matched general Danish population
- c) cohort-matched patients with AD not receiving systemic treatment (see section above for matching criteria).

Categorical covariates will be described by frequency distribution while continuous covariates expressed in terms of their mean and standard deviation or median and interquartile range (IQR) as appropriate. The descriptive statistics will be captured in a statistical report with aggregated data in tables.

Between group comparisons for baseline characteristics:

Pearson's chi-square test will be used for dichotomous categorical variables, t-test will be used for continuous variables, and the Mann-Whitney U test for non-parametric variables. The statistical analysis will be captured in a statistical report with aggregated data in tables.

Primary endpoint statistical analysis:

Incidence rates of major adverse cardiovascular events (MACE) and malignancy (excluding non-melanoma skin cancer (NMSC)) will be presented per 10,000 person-years at risk with 95% confidence intervals. The incidence rates will be reported for each group separately: a) a dermatologist-verified adult patient population with atopic dermatitis (AD) receiving conventional systemic treatments as per inclusion/exclusion criteria, b) cohort-matched general Danish population and c) cohort-matched patients with AD not receiving systemic treatment (see section above for matching criteria). For group a, the incident rates will be presented per individual conventional systemic treatment (see table II).

In cases where patients received two systemic treatments or more during the data collection period, each treatment series will be analyzed independently. The statistical analysis will be captured in a statistical report with aggregated data in tables.

In the primary analyses, overlapping events will be attributed to the drug to which the patient has been exposed for the longest duration.

Secondary endpoint statistical analysis:

Incidence rates of additional adverse events of special interest (All-cause mortality, Arterial thromboembolisms, Venous thromboembolisms, Dyslipidemia, Herpes zoster, NMSC, Serious infections) will be presented per 10,000 person-years at risk with 95% confidence intervals. The incidence rates will be reported for each group separately (Groups a) a dermatologist-verified adult patient population with atopic dermatitis (AD) receiving conventional systemic treatments as per inclusion/exclusion criteria, b) cohort-matched

general Danish population and c) cohort-matched patients with AD not receiving systemic treatment (see section above for matching criteria)).

For group a, the incident rates will be presented per individual conventional systemic treatment (see table II).

In cases where patients received two systemic treatments or more during the data collection period, each treatment series will be analyzed independently. The statistical analysis will be captured in a statistical report with aggregated data in tables.

In the primary analyses, overlapping events will be attributed to the drug to which the patient has been exposed for the longest duration.

Tertiary statistical analysis:

Comparison of the identified adverse events per individual conventional treatment (table II) with the following two matched groups: a cohort-matched general Danish population and a cohort-matched patients with AD not receiving systemic treatment (see section above for matching criteria).

The groups will be compared using a Cox-regression models. The proportionality assumptions will be tested using Schoefeld test and plots. If the PH assumption is violated, we will allow time-varying effects by including covariate $\times$ log(time) interactions or using time-split intervals. Use of competing-risk models will be employed where relevant and feasible. The statistical analysis will be captured in a statistical report with aggregated data in tables. In the primary analyses, overlapping events will be attributed to the drug to which the patient has been exposed for the longest duration.

P-values may be reported when relevant for descriptive purposes and will not be adjusted for multiple testing; they are presented as descriptive statistics only, and no hypotheses are being tested.

A sensitivity analysis will be conducted requiring only one use of a drug to fulfil the inclusion criteria.

To evaluate the robustness of the method applied to handle overlapping events in the primary analysis, multiple sensitivity analyses will be performed, in which overlapping events will alternatively be assigned to (a) the most recently administered drug, (b) attributed to both drugs, or (c) excluded by censoring the patient at the time of the event. These results will be presented separately.

Furthermore, a sensitivity analyses will be conducted reporting incidence rates for the years 1995-2001, 2002-2008, 2009-2015, and 2016-2022.

As a sensitivity analyses, a cox regression model with inverse Probability Treatment Weighting will be conducted.

Analyses will be conducted using SAS 9.4, Python v3.11.5, and R v4.4.1

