**Cohort entry (index date) for exposed:**

- 1) Date of initiation of the second administration/filled prescription of the conventional systemic therapy for AD,
- 2) Last inclusion date is December 31st, 2021, to allow for a minimum of one year of follow-up.

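### The tertiary comparison is per drug, but the protocol provides no matching, balance check or time zero per drug, so balance of each drug's hazard ratio is not assured

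*Protocol*

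**What the plan says.** **The comparison is per drug.** The tertiary objective (section 7), the tertiary endpoints (section 8.1) and the tertiary analysis (section 8.7) all ask for it: "Comparison of the identified adverse events per individual conventional treatment (table II) with the following two matched groups". Table II lists five conventional treatments.

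**The matching is described for treated patients as one body.** Section 8.1: "AD patients will be matched with individuals from the general population and patients with AD not treated with a systemic". Section 8.7, Matching, gives one propensity-score description: "The logit function may include, among others, age, sex, index date (prescription date of conventional systemic therapy", with at least one cardiovascular risk factor also named. Drug and line of therapy are not among the named variables.

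**The groups are one exposed and two comparator cohorts.** Section 8.7 defines group a as the "dermatologist-verified adult patient population with atopic dermatitis (AD) receiving conventional systemic treatments as per inclusion/exclusion criteria", followed by one group b and one group c. The split by drug is written for the exposed only: "For group a, the incident rates will be presented per individual conventional systemic treatment (see table II".

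**Later drugs count in their own right.** "In cases where patients received two systemic treatments or more during the data collection period, each treatment series will be analyzed independently". Exposure time is accumulated by the specific therapy, and a change to another conventional drug is not in the list of censoring events (section 8.7, follow-up).

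**The index date is written in the singular.** Section 8.2: "Date of initiation of the second administration/filled prescription of the conventional systemic therapy for AD". The intention-to-treat wording in section 8.7 (Events) assigns events to the treatment started at the index date, which implies one such date per patient.

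**The concern.** Propensity matching balances the covariates of the group that was matched. If that group is all treated patients, age, sex, calendar time and cardiovascular risk agree on average over the mix of five drugs. They need not agree for the users of any one drug. Where one drug's users are older or at higher cardiovascular risk than the treated average, a common comparator is too young or too healthy for them; for another drug the reverse holds. Part of the difference between the per-drug hazard ratios would then reflect who receives each drug.

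A second or later drug adds a problem of timing. Its events and person-time are analysed as a separate series, but no new time zero, covariate update or re-match is given for its start. The study period runs from 1995 to 2022, so the interval since the matched date can be long.

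Section 8.1 relies on matching to isolate the treatment's effect and to make the safety comparisons more reliable. For the per-drug hazard ratios, the text as it reads does not secure that.

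**Working it through.** **Plan's own figure.** The only size figure that can be recomputed is in section 8.2: 13,000 × 0.015 = 195 MACE per year, consistent with the stated more than 100. The point here does not depend on it.

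**Unit of analysis against unit of matching.**

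| Element | Stated for | Place |
|---|---|---|
| Hazard ratio | each drug | 8.7, tertiary analysis |
| Propensity model | conventional systemic therapy | 8.7, Matching |
| Baseline description | groups a, b, c | 8.7, patient characteristics |
| Incidence rates | group a by drug; b and c not split | 8.7, primary and secondary analyses |
| Time zero | second fill of the therapy, singular | 8.2, cohort entry |
| Weighted Cox sensitivity analysis | not stated as drug-specific | 8.7, end |

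No row supplies matching, a balance check or a time zero at drug level. Because baseline tables are by groups a, b and c, imbalance within a drug could go unseen.

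**Does pooled balance carry over to a drug?** This was checked by simulation. All inputs are assumptions except the roughly 1,000 patients per drug, which section 8.2 expects for most treatments.
- Treated: 5 drugs × 1,000; age SD 14; drug mean ages spread evenly over 42 ± 0, ± 5 or ± 10 years; cardiovascular risk factor in 6%, 10%, 12%, 15% and 25%; women 45% to 60%.
- Pool: 40,000 people, mean age 48, SD 18, risk factor 12%.
- One pooled logistic propensity score (age, age squared, sex, risk factor), 1:1 with replacement.
- Measure: SMD = (mean₁ − mean₀) / √[(var₁ + var₀)/2].

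Over the whole treated cohort, every |SMD| was at most 0.042. For the two extreme drugs:

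| Spread of drug mean age | Age, whole comparator | Age, own matched sets | CV risk, whole comparator | CV risk, own matched sets |
|---|---|---|---|---|
| ± 0 y | 0.02–0.04 | 0.03–0.05 | 0.24–0.28 | 0.16–0.21 |
| ± 5 y | 0.33–0.36 | 0.11–0.13 | 0.20–0.30 | 0.14–0.24 |
| ± 10 y | 0.63 | 0.06–0.14 | 0.29–0.33 | 0.28–0.29 |

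Pooled balance therefore does not ensure per-drug balance. Restricting each drug to its own matched sets removes most of the age imbalance where drug ages differ, but leaves |SMD| of 0.14 to 0.29 in cardiovascular risk.

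**What an age gap could do (illustration).** If event risk doubles every T years and a drug's users are d years older than a common comparator, the spurious ratio is 2^(d/T). With T from 10 down to 8: d = 3 gives 1.23–1.30; d = 5 gives 1.41–1.54; d = 8 gives 1.74–2.00.

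**A second drug started L years after the matched date.** If that drug's clock restarts and the comparator's does not, and rates rise by a proportion g per year of age, the ratio is (1 + g)^L. With g = 0.05 to 0.10: L = 1 gives 1.05–1.10; L = 3 gives 1.16–1.33; L = 5 gives 1.28–1.61. If both clocks run from the same index date, both sides age equally and this shift is absent.

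**The case against.** Four stronger readings are tempting, and the protocol does not support them.

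1. *A reader might infer that the protocol fixes a single match, to the pooled cohort, at the first drug's index date.* That is the natural reading but is nowhere stated. The inclusion criterion requires the same drug twice, which is a drug-specific trigger, and "index date (prescription date of conventional systemic therapy), and the presence of at least one cardiovascular risk factor" could be applied drug by drug.
2. *A reader might infer that no per-drug comparison is matched at all.* This goes too far. With 1:1 to 1:4 matching, each treated patient has their own comparators, so a first-line drug can be analysed within its own sets. What is lacking is any statement that this will be done, and any check that balance then holds.
3. *A reader might infer that a later drug necessarily carries an age shift.* It does so only if the comparator clock is not moved with the drug's clock. Follow-up is stated to run from the index date, and no reset is specified. In a model on time since index, comparators age in step; what remains is change in risk factors since the matched date.
4. *A reader might take the ratios above as estimates of bias.* They rest entirely on assumed age gaps and rates of increase.

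Two further arguments deserve weight. Covariates, caliper and algorithm can reasonably be left to an analysis plan, and that stands for those items. The unit of matching and time zero are different: the protocol addresses both itself, in a form that does not fit its objective. Second, the comparison is tertiary, the study is descriptive, and no hypotheses are tested. That limits the consequence, and the per-drug rates of the primary and secondary objectives do not depend on matching. The per-drug hazard ratios will still be reported, under a design said to isolate the effect of treatment.

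**Conclusion.** The concern holds as a mismatch between a per-drug comparison and matching that reads as being for the treated cohort as a whole. Following the text can leave each drug's hazard ratio unbalanced, with the weakest footing for second and later drugs. The weighted sensitivity analysis does not clearly close the gap, because it is not said to be drug-specific.

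The size of the bias cannot be derived from the protocol, which gives no age or risk profile by drug. The simulation shows that the mechanism is possible under assumed differences between drug users; it does not show how large those differences are in Denmark. If the drugs' users are alike on the matching variables at their own start dates, the practical effect is small. The point should be corrected before analysis, but it affects only the tertiary comparisons.

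**What to change.** In section 8.7 (Matching and the analysis paragraphs that follow), define the comparison separately for each Table II drug:

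- Set time zero at that drug's own qualifying second fill or administration, including when it is a patient's second or later drug.
- Match, or weight, comparators at that date, with covariates updated to it.
- Report standardized differences within each drug as well as for the whole treated cohort.
- Fit each drug's Cox model, and compute the comparator rates set beside it, in that drug's own matched sets, with both sides on the same clock.
- Keep the pooled rates for groups b and c as descriptive context.

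The cost is protocol wording and several runs of the same matching code (five if every drug is analysed separately) on registry data already held. Comparator rates have to be tabulated by drug, and some comparators will serve for more than one drug.
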